1°,2°,3° groups: after 2017 were allowed to enter in the study and were prospectively evaluated

supplementation omega-3

Group 1	Group 2	Group 3	Group 4 new onset	
	vs Group 1	vs Group 2	vs Group 3	
		vs Group 1	vs Group 2	

			vs Group 1	
2014	2015	2016	2017	2018

The analysis will allow to quantify the effects of omega-3 at different distance from the onset in terms of metabolic advantage (insulin units / Kg / die, glycated hemoglobin, etc.) and to evaluate if and how much supplementation after the onset may give metabolic advantages compared to other patients not yet supplemented.

To the T0, T3, T6 and T12 will be detected anthropometric parameters (weight, height, BMI, Tanner Stages, PAOS / PAOD), insulin therapy in progress (IU / Kg / die) with MDI (multiple daily injection) or CSII (continuous subcutaneous infusion) and metabolic parameters (C-peptide, coagulation, lipid profile, basal blood sugar, glycated hemoglobin, vitamin D). The C-peptide in particular allows us to evaluate the residual cell function, which provides a "direct" measurement of endogenous insulin secretion. The fasting C-peptide / glycemia ratio will also be evaluated, as an estimate of residual insulin secretion. Glycated hemoglobin is an expression of blood sugar in the last three months. A value of less than 7.5% is a sign of good compensation.

In addition, the glucometer data will be downloaded at each visit to evaluate the glycemc variability parameters (mean glycemia, DS). A DS of less than 50% of the mean blood glucose represents an index of stability. The use by all patients of the same meter, delivered at the time of inclusion in the study, will eliminate the bias given by the diversity of the medical device. Indication will be given to perform pre-meal glycemc controls three times a day, and occasionally after 2 hours from the meal, in order to calculate the glycemc variability.

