T.3 at 3 months from the beginning of the supplementation, only for the subjects supplemented with omega 3. Auxological and metabolic evaluation (IU / Kg / day exogenous insulin) by examination, blood tests (AA / EPA, C-peptide, basal glycemia, glycated hemoglobin, lipid profile, coagulation). Discharge of glucometer data for glycemic variability.

T.6 to 6 months from start of supplementation, only for subjects supplemented with omega 3. Auxologic and metabolic evaluation (IU / kg / exogenous insulin) by examination, blood tests (AA / EPA, C-peptide, basal blood sugar, glycated hemoglobin, lipid profile, coagulation). Discharge of glucometer data for glycemic variability.

T.12 At 12 months from the beginning of the study, will be re-evaluated for all subjects, all the previous auxological, metabolic and biochemical parameters and a new evaluation of the dietetic dike of fatty acids will be carried out.

Study security and caution of the subject included

The safety of the therapy with supplements is reflected in the extensive experience of using cod liver oil which in the past has been a routine supplement for children for several years.

High doses of Ω -3 over 5 g / day could result in a longer bleeding time, which is why coagulation monitoring is required, even if supplementation is required at doses of less than 5 g / day. With the use of Ω -3 a reduction of triglyceride levels is observed, which could represent a clinical advantage for the subject and a precise therapeutic objective often sought by the practitioners. A triglyceride evaluation will be performed pre-supplementation and at 12 months from the beginning of the same.

Financial resources and expected costs

01/01/2017

Enervit supplies Ener Zone Omega 3 RX in capsules containing each EPA 400 mg + DHA 200 mg and in liquid formulation for younger children and / or with concomitant celiac disease. Ascensia Diabetes Care supplies Conturnext USB and Conturnext strips, to allow frequent blood glucose measurements, with accuracy and precision.

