The blood chemistry tests are part of the normal T1D treatment routine. The dosage of the different metabolic and hormonal parameters at the time T1 will be borne by the Pediatric Clinic. The AA / EPA report will be determined by the Department of Pharmacological and Biomolecular Sciences DiSFEB, Faculty of Pharmaceutical Sciences of the University of Milan free of charge. Other possible findings as coagulation will be calculated as expenditure "study use" of the Pediatric Clinic.

DATA PROTECTION

to. Blood samples collected on Guthrie cardboard sent to Milan will be collected with the informed consent of the parents.

b. For the protection of the subject and clinical data, withdrawals will be identified with a code.

c. The clinical data will be managed by clinical referents inside Pediatrics ([name], [name]) and the name of the subject will be identified by initial name and surname

d. The withdrawals will be stored in the Laboratory of Milan Pharmacy University of the Maggiore Hospital under the exclusive control of the laboratory referents ([name])

Statistic analysis

The data will be expressed as a mean \pm SD. For continuous variables, the variations between the groups are compared by means of the averages calculated with the non parametric Wilcoxon and Mann-Whitney U tests. The variability of the biochemical parameters over time will be evaluated by means of tests for repeated measurements. A correlation analysis will be performed with the Pearson correlation test, after adequate logarithmic transformation of the parameters when necessary. Multiple regression analysis will be used to evaluate associations between variables. Statistical significance will be assumed for values of $p < 0.05$. All statistical analyzes will be performed with the SPSS program for Windows version 22.0 (SPSS INC; Chicago, IL, USA).

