## Statistic analysis

The data will be expressed as a mean  $\pm$  SD. For continuous variables, the variations between the groups are compared by means of the averages calculated with the non parametric Wilcoxon and Mann-Whitney U tests. The variability of the biochemical parameters over time will be evaluated by means of tests for repeated measurements. A correlation analysis will be performed with the Pearson correlation test, after adequate logarithmic transformation of the parameters when necessary. Multiple regression analysis will be used to evaluate associations between variables. Statistical significance will be assumed for values of  $p < 0.05$ . All statistical analyzes will be performed with the SPSS program for Windows version 22.0 (SPSS INC; Chicago, IL, USA).

All children with T1D with disease onset in the years 2017, will receive omega 3 supplement (EPA + DHA 60 mg / kg / of), and will be compared from a metabolic point of view (in particular for the needs of insulin and glycated hemoglobin) according to the scheme outlined with the pre-supplementation data, deduced from the medical records retrospectively.

supplementation omega-3 ↓

Group 1 n.	Group 2 n.	Group 3 n.	Group 4 new onset	
	vs Group 1	vs Group 2	vs Group 3	
		vs Group 1	vs Group 2	
			vs Group 1	
2014	2015	2016	2017	2018

The analysis will allow to quantify the effects of omega-3 at different distance from the onset in terms of metabolic advantage (insulin units / Kg / die, glycated hemoglobin, etc.) and to evaluate if and how much supplementation after the onset may give metabolic advantages compared to other patients not yet supplemented.

Further statistical analysis could be performed if appropriate.

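### Coagulation is monitored because of a named harm, but no analysis of it is specified beyond generic group-level methods, which can miss a change confined to a few children

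*SAP*

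**What the plan says.** The protocol section on study security says that omega-3 above 5 g/day might prolong bleeding time, "which is why coagulation monitoring is required, even if supplementation is required at doses of less than 5 g / day". Subjects and Methods lists coagulation for T0, T3, T6 and T12 among the "metabolic parameters (C-peptide, coagulation, lipid profile, basal blood sugar, glycated hemoglobin, vitamin D". The chronology section names it at T0, T3 and T6, restricts T3 and T6 to supplemented children, and repeats all earlier measurements in all subjects at T12. The section on financial resources charges coagulation to the study budget, apart from the routine blood tests.

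The statistics section, which is the same in the protocol and the SAP, mentions neither coagulation nor safety. Its general rules are:

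- Summary: "The data will be expressed as a mean" ± SD.
- Between groups: continuous variables are "compared by means of the averages calculated with the non parametric Wilcoxon and Mann-Whitney U tests".
- Over time: "The variability of the biochemical parameters over time will be evaluated by means of tests for repeated measurements".
- Associations: Pearson correlation, and "Multiple regression analysis will be used to evaluate associations between variables".
- Threshold: p<0.05.

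The SAP adds that further analysis is possible if appropriate. Neither document names a coagulation assay, a limit for an abnormal value, a count of children beyond it, a shift from baseline or a listing.

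**The concern.** The safety question is how many children move to an abnormal coagulation value, and whether they are those prescribed the most omega-3. A mean, an SD and a p-value for the group answer a different question. If an effect is confined to one, two or three children, the mean moves little, and those same children widen the SD that the test divides by.

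At stake is what the trial can say about the one harm it names, in children. Under the stated rules, the published coagulation result could be a nearly unchanged mean and a non-significant test while individual children had clearly abnormal values. The efficacy comparison is not affected.

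**Working it through.** **No figure to reproduce.** The documents give no sample size (the group sizes in the SAP scheme are blank), no coagulation SD, no limit and no expected number of affected children. The values below are assumptions, in units of the between-child SD at one visit: n = 20 to 60 supplemented children, k = 1 to 3 affected, each raised by s = 3 SD, within-child correlation r = 0.5 or 0.7, two-sided alpha 0.05.

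**Why the group test is weak.**

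- Mean change = k·s/n.
- SD of change ≈ √[2(1−r) + s²·p(1−p)], with p = k/n.
- Ratio = mean change ÷ (SD of change/√n), to compare with the t critical value.

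With r = 0.7, 2(1−r) = 0.6:

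| n | k | Mean change | SD of change | Ratio | Critical value |
|---|---|---|---|---|---|
| 20 | 1 | 0.15 | √(0.6+0.4275) = 1.01 | 0.66 | 2.09 |
| 30 | 2 | 0.20 | √(0.6+0.56) = 1.08 | 1.02 | 2.05 |
| 60 | 3 | 0.15 | √(0.6+0.4275) = 1.01 | 1.15 | 2.00 |
| 20 | 3 | 0.45 | √(0.6+1.1475) = 1.32 | 1.52 | 2.09 |

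The typical ratio is below the critical value in every row.

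**Simulated rejection rates, T0 against one follow-up, r = 0.7, 4,000 runs each.**

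| n | k | Wilcoxon | Paired t |
|---|---|---|---|
| 20 | 1 | 4.8% | 4.4% |
| 30 | 1 | 5.2% | 4.8% |
| 30 | 2 | 7.5% | 9.1% |
| 60 | 3 | 8.8% | 14.1% |

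These four give the range of about 4–14%. They leave out the combination kindest to the test, 3 of 20. I ran that as well: Wilcoxon 13%, paired t 17%. At r = 0.5 the same combination gives 13% and 16%.

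**Repeated-measures tests over T0, T3, T6 and T12** (shift present at all three follow-up visits). At r = 0.5, with one child affected, ANOVA and Friedman reject in about 4–5% of runs. With two, they reject in about 5–9%. With three, ANOVA rejects in 12–23% and Friedman in 5–8%. At r = 0.7, ANOVA with 3 of 20 reaches 28%, the highest rate found with a 3 SD shift. The change is therefore missed in at least 100 − 28 = 72% of runs, and in about nine in ten with one or two children.

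**Counting children instead.** Take an assumed upper limit of mean + 2 SD. A child raised by 3 SD exceeds it at one visit with probability Φ(3−2) = 0.84. At least one affected child exceeds it with probability 0.84 for k = 1, 1 − 0.159² = 0.97 for k = 2, and 1 − 0.159³ = 0.996 for k = 3. An unaffected child exceeds it with probability 0.023, so chance alone gives up to about 0.023 × 20 = 0.5 to 0.023 × 60 = 1.4 exceedances per visit. A count is not a test at the 5% level and must be read against T0.

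**What a count of zero would allow.** The exact two-sided 95% upper limit is 1 − 0.025^(1/n): 16.8% for n = 20, 8.8% for n = 40 and 6.0% for n = 60.

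**Prescribed intake.** At 60 mg/kg/day, assumed weights of 15, 40 and 80 kg give 0.9, 2.4 and 4.8 g/day. The 5 g/day mark is reached at 5000/60 = 83.3 kg. The supplementation section states no cap, while the section on study security describes doses below 5 g/day.

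**The case against.** The plan is not limited to a mean and a test over time. Rank tests, correlation and regression also cover continuous variables, regression could relate coagulation to intake, and further analysis is allowed. Clinicians will see individual results at visits. Outliers would show in the SD: with 2 of 30 children raised by 3 SD, the follow-up SD goes from 1 to √(1+0.56) = 1.25. The documents tie the harm to doses over 5 g/day and exclude children with coagulation defects. The study calls itself preliminary. Any test of a mean is weak against one or two outliers, so the simulation shows a general limit with assumed inputs.

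Much of this stands, and it rules out several stronger readings that a reader might infer:

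- *Coagulation will be analysed only as a pooled mean and a time test.* Neither word is supported. The scheme is organised by onset-year group, other methods are listed, and applying the sentence on biochemical parameters to coagulation is itself an inference.
- *The trial will report the harm as absent.* Nothing says that a non-significant mean will be read that way.
- *Each child's own T0 value is the only usable comparator.* This is unsettled. The supplementation section gives omega-3 to all patients with recent onset. The chronology starts it in case of deficiency and willingness, and re-evaluates all subjects at T12, so unsupplemented children with T0 and T12 values may exist. That historical records lack coagulation is only an inference from the budget line.

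What does not stand is that these points close the gap. The listed methods are all group-level or are not assigned to coagulation or intake. At T3 and T6 no unsupplemented child is scheduled. Permission for further analysis commits to nothing. A wider SD does not tell a reader how many children were abnormal or at what prescribed intake. The protocol itself requires monitoring below 5 g/day.

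**Conclusion.** The point holds in this form: coagulation is collected because of a named harm, and no analysis suited to that question is specified. The generic methods would usually miss a change confined to one to three children. The rejection rates (about 4–17% for paired tests, at most 28% for repeated-measures ANOVA) rest on the assumed n, number affected, 3 SD shift, correlation and normal values. They illustrate the mechanism and do not predict this trial's result. The plan should be changed, since the matter concerns safety in children and the remedy is cheap, but no efficacy conclusion depends on it. The two dose statements must be reconciled separately. The documents do not settle which governs, and this review takes no position on that.

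**What to change.** In the statistics section of both documents, add a short safety analysis for coagulation:

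1. Name the coagulation assays.
2. For each assay at T3, T6 and T12, report the number and percentage of supplemented children outside the laboratory's age-appropriate reference range, with exact 95% CIs.
3. Give a shift table from each child's T0 category.
4. List or plot each child's change from T0 against prescribed EPA + DHA in g/day (60 mg/kg times recorded weight). Label it prescribed intake, because no adherence record is described.
5. Report unsupplemented children alongside at T12, if any have values.
6. State that a non-significant mean change will not be read as absence of a coagulation effect.

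Separately, reconcile the supplementation section (60 mg/kg/day, no cap stated) with the section on study security (doses below 5 g/day).

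The cost is a few lines of text and a few tables or plots. Coagulation and weight are already scheduled, so no visit or test is added. The small downside is that the counts will include some chance exceedances, which is why the T0 shift table belongs beside them.

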Usually the honeymoon phenomenon is exhausted within a year, even if a residual amount of secretion persists at least up to two years from the onset. The endogenous insulin secretion is quantifiable as C-peptide, which represents the conjugation peptide between chain A and B of pro-insulin, which after free cleavage in the portal circle molecules of C-peptide and insulin in molar ratio 1: 2. Unlike insulin that is rapidly degraded in the liver and tissues, the C-peptide passes the liver and is filtered by the unchanged renal glomeruli in the urine. C-peptide is not present in exogenous insulin of pharmacological origin. The endogenous insulin secretion is quantifiable as C-peptide. A persistence of C-peptide (also dosages 0.2 ng / ml) reduces the risk of complications, improves the metabolic compensation and reduces the number of hypoglycemic episodes, so at least one of its maintenance would be an important objective to preserve.

01/01/2017

The study is preliminary and aimed at identifying whether a therapy with Ω -3 could be of support in T1D especially in the first years of illness, when a persistence of a residual β -cell mass is presumable and it is possible to act better on the pro-inflammatory component (insulinitis).

Purpose of the study

The aim of the study is to evaluate whether a controlled administration of vitamin D and Ω -3, in the early years of the onset of T1D, can preserve the residual β -cell mass, evaluable with a reduced insulin need for a long time, with a persistent level of C-peptide, a lower glycemic variability compared to children who do not carry out this supplementation.

Secondary assessment is to perform a baseline assessment of the AA / EPA ratio in children with type 1 diabetes.

Subjects and Methods

The subjects will be recruited at the Diabetology Clinic of the Pediatric Clinic of the AOU "Maggiore della Carità" of Novara.

In particular, two groups of subjects will be included, subject to the signing of the informed consent:

1°,2°,3° the groups, with T1D onset in 2014, 2015, 2016, retrospectively were evaluated as historical controls before 2017.

4 group°: all children with T1D with disease onset in the years 2017, will receive omega 3 supplement (EPA + DHA 60 mg / kg / of), and will be compared from a metabolic point of view (in particular for the needs of insulin and glycated hemoglobin) according to the scheme outlined with the pre-supplementation data, deduced from the medical records retrospectively.

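### The plan sets out to quantify omega-3 effects by time since onset, but its separate pairwise rank tests neither estimate an effect nor test whether it differs by time since onset

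*SAP*

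**What the plan says.** The SAP (Statistic analysis) gives the aim: "The analysis will allow to quantify the effects of omega-3 at different distance from the onset in terms of metabolic advantage". The same sentence adds that the study will judge whether, and by how much, starting after onset helps relative to children who have not started. The group scheme, which also appears in the protocol under Subjects and Methods, has six cells: Group 2 against Group 1; Group 3 against Groups 2 and 1; Group 4 against Groups 3, 2 and 1. The comparison is to be made "according to the scheme outlined with the pre-supplementation data, deduced from the medical records retrospectively".

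On method, the SAP says that "the variations between the groups are compared by means of the averages calculated with the non parametric Wilcoxon and Mann-Whitney U tests". The threshold is given by "Statistical significance will be assumed for values of" p<0.05, with no rule for multiple tests. Three further statements could bear on the question:

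- "The variability of the biochemical parameters over time will be evaluated by means of tests for repeated measurements"
- "Multiple regression analysis will be used to evaluate associations between variables"
- "Further statistical analysis could be performed if appropriate"

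None of them names an omega-3 term, a time-since-onset term or an interaction. No cohort size, effect size or power is stated.

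**The concern.** How the effect varies with time since onset is a question of effect modification. Answering it takes an estimated effect at each distance and a comparison between those estimates. A rank-test p-value for each cell supplies neither. A p-value below 0.05 in one cell and above it in another does not show that the two effects differ, because the same true effect can easily produce that pattern when cohorts are small.

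At stake is a message about when to supplement. The protocol says "The study is preliminary and aimed at identifying whether a therapy" with omega-3 could help, particularly in the first years of illness. A statement that it works early but not late, or the reverse, is a likely product of such a study, and the named analysis could not support it.

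**Working it through.** There is no sample-size or power figure in the plan to reproduce. The check asks how often separate tests disagree when the true effect is the same at every distance.

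**Inputs from the SAP:** the six-cell scheme, Mann-Whitney tests and the 0.05 threshold.

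**Assumptions:** two-sided tests; normal outcomes; equal cohorts of 20 or 30; a true effect of 0.5, 0.7 or 0.9 SD at both distances; within-child correlation 0.6. The scheme is read as matched on time since onset: Group 4 at the earliest distance, Group 3 at the next, Group 2 at the latest, each against earlier cohorts before supplementation.

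**Step 1. Independent comparisons.** If each has power p, the chance that exactly one of two is significant is 2p(1-p).

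- No effect: 2 × 0.05 × 0.95 = 9.5%.
- n=20, 0.5 SD (simulated power 0.325): 2 × 0.325 × 0.675 = 44%.
- n=30, 0.5 SD (simulated power 0.448): 2 × 0.448 × 0.552 = 49%.

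The quantity peaks at 50% when p = 0.5, so intermediate power is what drives it.

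**Step 2. Shared Group 1 controls.** Take Group 4 vs 1 and Group 2 vs 1, with the same Group 1 children measured at two durations. Each contrast has variance 2σ²/n and their covariance is ρσ²/n, so their correlation is ρ/2 = 0.3. Positive correlation makes the two tests agree more often. At n=20 and 0.5 SD, simulated discordance is 36%. The implied chance that both are significant is (2 × 0.325 - 0.36)/2 = 0.145, against 0.325² = 0.106 under independence.

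**Step 3. Simulated chance that exactly one of two is significant** (ranges span repeated simulations; 4,000 runs give a Monte Carlo error of about 0.8 percentage points):

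| n per cohort | True effect | Shared Group 1 controls | Independent controls |
|---|---|---|---|
| 20 | 0.5 SD | 36% | 44% |
| 20 | 0.7 SD | 39-42% | 49-51% |
| 20 | 0.9 SD | 29-31% | 35% |
| 30 | 0.5 SD | 40-41% | 50% |

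With no effect and n=20 the figure is about 9%.

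**Step 4. Three distances, each against Group 1** (within-child correlation 0.5). With an equal effect, a mixed pattern appears in 36%, 56% and 63% of runs at 0.5 SD, and in 60%, 57% and 35% at 0.8 SD, for n = 10, 20 and 30. With no effect it appears in 13-15%. A single direct contrast of the earliest and latest effects is falsely significant in 4.6-7.0% of runs, the small excess coming from a z approximation.

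**Step 5. Unequal numbers of tests.** The scheme gives the earliest distance three tests, the next two and the latest one. Suppose a distance is called positive when any of its tests passes 0.05, a rule the plan does not state. At n=20 with an equal 0.5 SD effect, early-but-not-late then occurs in 37% of runs and late-but-not-early in 14%.

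**The case against.** The strongest reply is that the SAP never says differing p-values will be read as differing effects. The aim can be taken as a separate comparison at each distance against children not yet supplemented, and repeated-measures tests, regression and further analyses are all mentioned. That is fair. A reader might infer that the plan commits the investigators to an early-versus-late conclusion from significance patterns, or that it rules out anything but rank tests; the documents support neither. What remains is that a separate comparison at each distance still needs an effect estimate, and the generic methods are not tied to this question.

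A reader might also infer that reusing the same children manufactures the false pattern. For shared Group 1 controls the opposite holds: sharing lowers discordance, from 44% to 36% at n=20 and 0.5 SD. An exception is a pair such as Group 2 vs 1 with Group 4 vs 2, where Group 2 changes sides: the correlation is -0.3 and discordance is about 51% in that setting. The +0.5 correlation between Group 4 vs 1 and Group 4 vs 2 is beside the point, because both sit at the same distance from onset.

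Finally, the percentages rest on assumed sizes and effects, and discordance is not itself a wrong conclusion. Both points stand.

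**Conclusion.** The point holds as a gap between the stated aim and the named analysis. The plan promises effects by time since onset, but its between-group tests give no effect size and no comparison across distances, so a mixed pattern could be misread. With 20 to 30 per cohort and an equal effect of 0.5-0.9 SD, two comparisons disagree in about 29-42% of runs with shared Group 1 controls and 35-51% with independent controls; with no effect at n=20, about 9%. The exact figures depend on the assumed cohort size, effect and within-child correlation, and limited power is the main cause. They measure how readily a misleading pattern arises, not how often the investigators would draw the wrong conclusion.

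**What to change.** For each main outcome (insulin in IU/kg/day and HbA1c), pre-specify one mixed model with:

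- a random effect per child;
- a time-varying omega-3 indicator (0 before that child's start, 1 after);
- time since diagnosis;
- an omega-3 by distance-from-onset interaction.

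Restrict it to distances where the scheme has both supplemented and not-yet-supplemented children; supplemented Group 1 has no comparator. Report the effect with a 95% CI at each distance and the interaction with its CI. Label the interaction exploratory, and claim a distance-dependent effect only if it supports one. Keep the six pairwise tests as description.

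The cost is SAP wording and some analysis time in the SPSS package already named, using data the study already plans to hold. There are three downsides to state:

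- **Wide intervals.** For a simple early-versus-late contrast against Group 1 at n=20, the half-width is 1.96 × √(4/20) = 0.88 SD with independent controls, or 1.96 × √(2.8/20) = 0.73 SD with shared controls at ρ = 0.6, since 2 + 2(1 - 0.6) = 2.8.
- **Confounding.** Distance at start nearly coincides with onset-year cohort, so calendar-year differences from historical controls remain and must be acknowledged.
- **Uneven visits.** The protocol's chronology limits T3 and T6 to supplemented children, and comparator data come from medical records.
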